8.3. Description of the statistical methods foreseen and the planned intermediate assessments

Descriptive data analyses will be performed using Statistical Package for Social Sciences SPSS 17.0® (SPSS Inc., Chicago, IL, USA). In order to compare efficacy of the intervention arms, the primary outcome will be the frequency of patients

achieving response to psychomotor retardation (i.e. >30% improvement from SRRS baseline scores). This group statistic will be calculated using Chi²-Tests.

In order to investigate the effect of rTMS on the psychomotor performance of participants, we will analyze changes in motor variables within and between groups using repeated measures-ANOVAs. This way, we will test for time effects and effects of stimulation protocol. In case of unequal distribution of descriptive parameters between groups, these parameters will be entered as covariates to the repeated measures ANCOVA. Before performing ANOVAs, a normalizing transformation will be carried out if necessary.

The same procedure will be followed in case of the diagnose specific symptoms ratings (BDI, MADRS, Hamilton, PANSS, SANS, CAINS).

To control if a possible improvement of psychomotor performance after rTMS may be attributed to a general clinical response, we will use the analysis of covariance (ANCOVA) with psychomotor performance ratings (before and after TMS) as within subjects factor and changes in ratings of diagnose specific symptoms ratings as covariate.

At three major recruitment steps (25% of total sample, 50% and 75% respectively) we will calculate the primary analysis. If one group proves to have significantly poorer outcome than the others, we will stop this study arm.

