Ghozlan, 1989). The gross motor activity will be furthermore assessed by actigraphs. Actigraphy is a method of quantitative assessment of motor behavior. Patients wear continuously a wrist actigraph, which records the gross motor activity in naturalistic settings. The baseline screening of patients for motor abnormalities will be based on ratings of Bern Psychopathology Scales (BPS), a validated quantitative and qualitative scales for the assessment of system-specific psychotic symptoms of three main domains: motor behavior, language and affectivity.

Fine motor performance The assessment of fine motor performance is based on a finger tapping test, during which, participants are asked to tap their index finger against their thumb as fast as possible in ten seconds. After a short period of practice, three periods will be measured and videotaped. An analysis of the tapping is additionally conducted in slow motion (Barkemeyer et al., 1998).

Gesture Performance The Test of upper limb apraxia (TULIA) (Vanbellingen et al., 2010) is a standardized examination of gesture performance that covers both pantomime and imitation domains and multiple semantic features.

Rationale and aim of the study

Psychomotor retardation is often reported by patients diagnosed with schizophrenia or MDD. Various brain regions may contribute to psychomotor slowing, but the pathophysiology still remains unclear. The effect of TMS of various stimulation parameters at different stimulation sites may lead to improved motor performance. Across diagnoses, patients with motor retardation will benefit from inhibitory stimulation over SMA. Taking into account findings of previous studies, the aims of the study are

- a. To assess the effects of the 3 weeks of daily TMS sessions on motor performance in patients with schizophrenia or MDD (fine motor activity, gross motor activity and gesture performance).
- b. To compare the psychomotor symptoms improvement between different TMS protocols
- c. To assess the effect of daily TMS in different configurations on other non-motor symptoms e.g. depressive symptoms, negative symptoms.

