4.1. Targeted primary end point and secondary end points (effectiveness and safety parameters)

Main objective is the effect of TMS on psychomotor retardation (PR) in patients with major depressive disorder or schizophrenia. Primary outcome marker will be the change in psychomotor performance as assessed by Salpêtrière Retardation Rating Scales (SRRS). Clinical response will be defined as a 30% reduction of the SRRS baseline scores.

Secondary targets will be the effect of TMS on other motor parameters and on specific symptoms e.g. depressive or negative symptoms.

Efficacy parameters: TMS parameters may be of critical role determining the effect of the applied TMS on motor symptoms.

Safety parameters: As specific safety factors in relation to TMS, patients with 1. past history of epilepsy, or 2. other increased neuronal activity in Electroencephalography (EEG), 3. MRI contraindications and 4. substance misuse will be excluded. EEG recordings will be held for all patients before the beginning of TMS. Patients will be screened every 5 sessions with SRRS and actigraphy. In case of moderate deterioration of motor performance (30% change of initial ratings of SRRS or/and actigraphy) or adverse reactions during the TMS protocol, patients will be excluded from further participation in the study. .

4.2. Specification of the parameter that is of primary interest and other parameters that will be assessed as additional, secondary end points.

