6.1. Effectiveness parameters: measuring methods and reference dates

The efficacy of TMS sessions will be evaluated primarily as improvement in SRRS baseline score after treatment. Furthermore, we investigate the effect of TMS on gross motor behavior (SRRS, actigraphy), fine motor function (finger tapping test), and hand gesture performance (TULIA). To this purpose, clinical ratings will be assessed twice, at baseline and after the last TMS **session**. Furthermore, changes may be demonstrated by the scales assessing the disorder specific symptoms; in patients with major depressive disorder, HAMD, MADRS and BDI, in patients with schizophrenia PANSS, SANS, CAINS and the Bush Francis Catatonia Rating Scales. Statistical analysis will comprise repeated measures ANOVAs of motor variables and stimulation mode as between subject variable. Clinical response will be defined as a 30% reduction of the SRRS scores.

7. Assessment of safety

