8.5. Handling of missing data, dropout cases

Only complete data records with assessments at two time points will be entered in the analyses. In case of dropout we will perform an intention-to treat (ITT) analysis applying the last-observation-carried-forward method (LOCF). In case of revocation of patients (KlinV, Art.9), data will be anonymized.

9. Study-specific safety precautions and responsibilities

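### The repeated-measures ANOVA plan does not name the stimulation mode × time interaction, so the between-arm test for the motor and symptom scores is left open and, read literally, is a weaker test that does not compare change

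*Combined protocol and SAP*

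**What the plan says.** The primary outcome in 8.3 is the frequency of SRRS response (more than 30% improvement from baseline), and for it "This group statistic will be calculated using Chi²-Tests". For the continuous measures, 8.3 states that "we will analyze changes in motor variables within and between groups using repeated measures-ANOVAs". The next sentence lists what this tests: "This way, we will test for time effects and effects of stimulation protocol". The depression, psychosis and negative-symptom scales are treated alike: "The same procedure will be followed in case of the diagnose specific symptoms ratings".

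Section 6.1 gives the model: "Statistical analysis will comprise repeated measures ANOVAs of motor variables and stimulation mode as between subject variable". It follows a statement that efficacy is judged first by improvement in the SRRS score, so the continuous SRRS score falls under this analysis too. The project summary in section 3 and sections 3.2, 4.2 and 8.1 mention ANOVAs with stimulation mode as the between-subject variable, without calling them repeated measures.

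On time points, 6.1 has the clinical ratings taken twice, at baseline and after the last session, and 8.5 says "Only complete data records with assessments at two time points will be entered in the analyses". Aim b in 3.1 is "To compare the psychomotor symptoms improvement between different TMS protocols". No section mentions an interaction or designates one term as the between-arm test.

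**The concern.** A pre/post ANOVA with a four-level group factor gives three tests: time, group, and group × time. The two effects listed in 8.3 match the names of the first two. Only the third asks whether patients changed more in one arm than in another, which is what aim b requires.

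The group main effect compares arms on the average of the baseline and post-treatment scores. Baseline precedes stimulation, so randomisation makes its expected difference between arms zero. The average therefore dilutes the treatment difference by half and retains the stable differences between patients.

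This is the only between-arm analysis given for actigraphy, finger tapping, TULIA and the symptom scales listed in 8.3. An analyst following the list literally could miss a real difference. An analyst choosing among the F-tests after seeing the data could say that any of them followed the plan.

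**Working it through.** **The plan's own figure.** The only power calculation (8.2) is for the chi-square test. With 25/25/40/10% against 25% each:

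- w² = (0.15² + 0.15²)/0.25 = 0.18, so w = 0.424.
- The critical value on 3 df is 7.815. 90% power needs λ = 14.17, so N = 14.17/0.18 = 78.7, rounded up to 79.
- At N = 79, λ = 79 × 0.18 = 14.22 and power is 90.1%.

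The stated figures reproduce. The documents give no power, SD, effect size or pre/post correlation for the ANOVAs.

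**Inputs for the ANOVA check.** From the documents: four arms of 20 (3.2), two time points (6.1, 8.5), α = 0.05 (8.4). Assumed: equal variances (SD = 1), pre/post correlation ρ from 0 to 0.8, one arm better by d = 0.8 SD after treatment and the other three equal, no dropout, no arm stopped.

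**Formulas.**

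- Group main effect: tests (pre + post)/2. Effect d/2, variance (1 + ρ)/2.
- Interaction: tests post − pre. Effect d, variance 2(1 − ρ).
- Baseline-adjusted post score (ANCOVA): effect d, residual variance 1 − ρ².

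The post-treatment means (0.8, 0, 0, 0) have mean 0.2, so SS = 20 × (0.6² + 3 × 0.2²) = 20 × 0.48 = 9.6. Hence:

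- λ(main) = (9.6/4)/((1 + ρ)/2) = 4.8/(1 + ρ)
- λ(interaction) = 9.6/(2(1 − ρ)) = 4.8/(1 − ρ)
- λ(ANCOVA) = 9.6/(1 − ρ²)

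The ratio λ(main)/λ(interaction) is (1 − ρ)/(1 + ρ), whatever the effect size. Power is from the noncentral F with 3 and 76 df; for ANCOVA this is approximate, since the covariate costs one further df.

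| ρ | λ main | λ interaction | ratio | power main | power interaction | power ANCOVA |
|---|---|---|---|---|---|---|
| 0 | 4.80 | 4.80 | 1.00 | 40.5% | 40.5% | 71.8% |
| 0.3 | 3.69 | 6.86 | 0.54 | 31.7% | 55.6% | 76.2% |
| 0.5 | 3.20 | 9.60 | 0.33 | 27.8% | 71.8% | 84.5% |
| 0.7 | 2.82 | 16.00 | 0.18 | 24.8% | 92.1% | 95.8% |
| 0.8 | 2.67 | 24.00 | 0.11 | 23.6% | 98.8% | 99.4% |

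Simulation (20,000 trials per setting) agrees: at ρ = 0.5, 27.6% for the main effect and 71.3% for the interaction. With no treatment effect, at the same ρ, the rejection rates are 5.3% and 4.9%, so both tests hold their level.

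**Without fixing d.** If the effect is scaled so that the interaction has 90% power, the main effect has 90% at ρ = 0, 63% at 0.3, 42% at 0.5, 23% at 0.7 and 16% at 0.8.

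**The case against.** The strongest reply is that the listed sentence should be read with the one before it, which says that changes are analysed within and between groups. Change compared between groups is the interaction, and aim b points the same way. A reader might infer that the plan commits to two main effects and excludes the interaction. The documents do not support that: they never use the term main effect and never limit the model to main effects. The sections that say only ANOVA are also no evidence of a wrong term, because if the variable analysed there is change, the mode effect is already the right test. What stands is that the sentence naming the tests omits the one that matters, and nothing else supplies it.

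A reader might also infer that most of the power is necessarily lost. It is not: at ρ = 0 nothing is lost, and from 90% interaction power more than half is lost only from about ρ = 0.5. Such a correlation is plausible for repeated ratings, but it is not in the documents.

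Nor is there a false-positive problem. A chance baseline difference can contribute to the main effect, but under randomisation that test still rejects at its nominal 5%.

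Finally, for SRRS and actigraphy there are interim ratings: "Patients will be screened every 5 sessions with SRRS and actigraphy". If these entered the model as four time points, the averaged effect would be 0.5d under linear onset or 0.75d under immediate onset, and the 9-df interaction would not always be the stronger test (d = 0.8, ρ = 0.3, immediate onset: main effect 80%, interaction 56%). But the interim ratings are described as safety screening, and 8.5 refers to two time points.

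**Conclusion.** The point holds as a specification gap. The between-arm test for the continuous motor and symptom scores is not identified, and the literal reading gives a term that carries half the treatment difference and does not answer aim b. On that reading its noncentrality is (1 − ρ)/(1 + ρ) of the interaction's. The power figures rest on an assumed effect of 0.8 SD in one arm, an assumed ρ, equal variances and 20 complete patients per arm.

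They do not carry over to the diagnosis-specific scales: HAMD, MADRS and BDI are given to patients with MDD, and PANSS, SANS and CAINS to patients with schizophrenia, so each is rated in only part of the 80.

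It would be wrong to conclude that the primary analysis is undermined. SRRS response is already defined on change and compared between arms by chi-square, and the N of 79, rounded to 20 per arm, rests on that test alone. This should be fixed for the secondary and continuous-score analyses, including the SRRS score where 6.1 places it in the ANOVA. It is not a defect that the trial cannot proceed with.

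**What to change.** Add to 6.1 and 8.3, in words such as:

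> For each motor variable and symptom scale, the between-arm test is the comparison of the post-treatment score between stimulation modes, adjusted for the baseline value of the same measure (ANCOVA). The between-subject main effect of a repeated-measures ANOVA is not interpreted as efficacy.

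If the sponsor prefers to keep the repeated-measures ANOVA, name the stimulation mode × time interaction over the two time points (equivalently, the comparison of change between arms) as the between-arm test, and keep the second sentence. The baseline-adjusted form is preferable because it was the most powerful of the three tests at every ρ examined, most clearly at low ρ, where the interaction is itself weak. The covariate provision already in 8.3 does not meet this need, since it applies only to descriptive parameters found unequal between groups.

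The cost is one or two sentences in each section, settled before the data are analysed. No extra patients, visits or measurements are needed.

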displaying reduced levels of motor activity. Diagnoses will be given through application of MINI and review of the complete cases files. Only patients displaying reduced levels of motor activity assessed with Bern Psychopathology Scales (BPS) will be included and will be randomly assigned to four equal groups. Patients will be informed about the stimulation procedure and the goals of the study. Written informed consent will be obtained. Female patients will take a urine pregnancy test before the beginning of the TMS sessions and they will be required to use contraceptive methods during the TMS protocol in order to enroll in the study. In case of a suspicion of a pregnancy during the study despite the use of contraceptives a urine test will be taken. Subjects will undergo a series of diagnostic tests assessing primarily different psychomotor domains and secondarily disorder specific symptoms. Questions concerning demographic data (age, gender, education, occupational status) as well as substance use and medication will also be included. Each group will receive sessions of TMS of different stimulation parameters. Regardless of the type and the frequency of TMS, the stimulation protocol will consist of 15 daily sessions during a 3 week period. The four different stimulation conditions have been described above. Subjects will be reassessed after TMS.

Following assessments will be performed:

- Mini-International Neuropsychiatric Interview (MINI) – A validated structured diagnostic psychiatric interview.
- Bern Psychopathology Scales (BPS) – A validated quantitative and qualitative scales for the assessment of system-specific psychotic symptoms
- Actigraphy – gross motor activity levels will be recorded by wrist actigraphs
- Salpêtrière Retardation Rating Scales (SRRS) – A validated scales allowing the assessment various domains of psychomotor performance including gait, gross and facial motorics, speech and cognitive elements
- Finger tapping test – video-taped assessments of fine motor performance
- Test of Upper Limb Apraxia (TULIA) –video-taped, blinded ratings of gesture performance
- Patients with Major Depressive Disorder (MDD): Hamilton Rating Scale for Depression (HAMD), Montgomery Åsberg Depression Rating Scale (MADRS), Beck Depression Inventory (BDI) (Beck et al., 1961),

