4.4. Measures to minimize bias risk

After recruitment patients will be randomly allocated to four groups. Groups will be matched for age, gender, education and diagnose. Rater is blinded, patient is semi-blinded (has no knowledge of TMS, but could however find out where stimulation occurs).

5. Selection of the participants

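### Section 8.3 adjusts the continuous analyses only if the arms look unequal, which loses precision and leaves the model open; secondarily, the 1 Hz SMA hypothesis has no named contrast or multiplicity rule

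*Combined protocol and SAP*

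**What the plan says.** For the primary outcome, section 8.3 states "In order to compare efficacy of the intervention arms, the primary outcome will be the frequency of patients" with more than 30% SRRS improvement, and "This group statistic will be calculated using Chi²-Tests". Section 8.2 sizes this as a four-group test with 3 degrees of freedom: 79 patients for 90% power, hence 20 per arm.

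The continuous motor variables go into repeated-measures ANOVAs for time and stimulation protocol. Covariates are conditional: "In case of unequal distribution of descriptive parameters between groups, these parameters will be entered as covariates to the repeated measures ANCOVA". The diagnosis-specific symptom ratings follow the same procedure. A further ANCOVA takes "changes in ratings of diagnose specific symptoms ratings as covariate".

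Four other places bear on this:
- Section 4.3, Study Design, lists possible descriptive parameters: "Questions concerning demographic data (age, gender, education, occupational status) as well as substance use and medication will also be included".
- Section 4.4 says "Groups will be matched for age, gender, education and diagnose".
- Section 8.5 says "Only complete data records with assessments at two time points will be entered in the analyses", and section 6.1 likewise places the clinical ratings at baseline and after the last session.
- Section 4.1 says "Primary outcome marker will be the change in psychomotor performance as assessed by" the SRRS, whereas sections 4.2, 8.1 and 8.3 make the primary outcome a response above 30%.

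The project summary in section 3 and sections 3.1 and 3.3 predict benefit from inhibitory stimulation over the SMA. Section 8.4 gives only a 0.05 level. Section 8.3 repeats the primary analysis at 25, 50 and 75% of recruitment and may stop an arm.

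**The concern.** The covariate set depends on observed imbalance, and neither the candidate list nor the criterion is stated. It is also unclear whether the outcome's baseline score counts as a descriptive parameter. Imbalance is a poor reason to pick a covariate, because what brings precision is how well it predicts the outcome. The better the matching in section 4.4 works, the less likely the matching factors are to enter. With 20 per arm, unused baseline information costs power in every continuous analysis.

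The second gap concerns the arm-specific hypothesis. A significant four-group test shows that the arms differ somewhere. It does not show that 1 Hz SMA stimulation beats sham. Any such statement would rest on a comparison whose test and error control were chosen afterwards.

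**Working it through.** **1. The plan's own figure.** From the responder shares in section 8.2 (25, 25, 40 and 10% against 25% each), w = √[(0.15² + 0.15²)/0.25] = √0.18 = 0.424. Then λ = 79 × 0.18 = 14.22. With a critical value of 7.81 (3 df) the power is 0.901, so the 79 reproduces.

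**2. Change score against ANCOVA.** Inputs are 20 per arm (8.2) and two time points (6.1, 8.5). The pre/post correlation ρ is not given and is assumed, with equal variance σ² at both times. I take the group-by-time interaction as the test of treatment effect; with two time points it is the change-score comparison.
- Change-score variance: 2σ²(1 − ρ)
- Baseline-adjusted variance: σ²(1 − ρ²)
- Ratio: (1 + ρ)/2

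The simulation used 6,000 trials of 4 × 20 per setting. Age, gender, education and diagnosis were assumed unrelated to outcome. Power is for the 3-df test when one arm improves by an assumed 0.8 SD.

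| ρ | (1+ρ)/2 | Simulated ratio, baseline only | Simulated ratio, baseline + 4 factors | Power, change score | Power, baseline only | Power, baseline + 4 |
|---|---|---|---|---|---|---|
| 0.3 | 0.65 | 0.66–0.67 | 0.68–0.69 | 56% | 76% | 74% |
| 0.5 | 0.75 | 0.77 | 0.79–0.80 | 72% | 83% | 82% |
| 0.7 | 0.85 | 0.86–0.87 | 0.89–0.90 | 92% | 96% | 95% |
| 0.9 | 0.95 | – | 0.985–1.005 | – | – | – |

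**3. The conditional rule.** Suppose unequal meant p<0.05, with independent tests. Some covariate would then enter by chance in 1 − 0.95³ = 14% of trials (the three listed parameters that are not matched), or in 1 − 0.95⁷ = 30% (all six plus diagnosis, ignoring matching). Simulated type I error under such a rule was 0.037–0.047. If covariates explained an assumed 20–50% of the variance of the analysed score, with one arm shifted 0.9 SD, power was 0.82–0.83 with conditional entry and 0.885–0.987 with prespecified entry.

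**4. A chance baseline gap.** The standard error between two arms is √(2/20) = 0.316 SD. A gap of 0.5 SD gives t = 1.58, p = 0.12, and a gap larger than that arises in 11% of pairs. Given such a gap, the change-score difference is off by (1 − ρ) × 0.5 = 0.35, 0.25 or 0.15 SD at ρ = 0.3, 0.5 or 0.7.

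**5. Error rates for arm-specific claims.** This is an exact enumeration of all 21⁴ outcomes, using uncorrected Pearson tests at one final look. Response rates are assumed.

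| All arms equal at | 25% | 30% | 40% | 50% |
|---|---|---|---|---|
| Any of six pairs, ungated | 20.0% | 21.4% | 19.2% | 16.9% |
| Any of three v sham, ungated | 12.7% | 13.3% | 12.0% | 10.6% |
| Four-group test | 5.0% | 5.1% | 5.0% | 4.9% |

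A gate on the four-group test, which the plan does not state, holds this near 5% when all arms are equal. When one arm works (assumed 50–80% against 20–40%), false positives among the three equal arms are still 10–13%. Holm over the three comparisons with sham after the gate gives 3–4%. If the four-group test is run at all four looks at 0.05, ignoring arm stopping, 11–13% of trials show at least one significant result with all arms equal.

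**6. Power with 20 per arm.** Arm rates are 4 × share × overall rate (at 25% overall: 40, 25, 25 and 10%), with 1 Hz SMA taken as best and sham as worst.

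| Overall response | 25% | 30% | 40% | 50% |
|---|---|---|---|---|
| Four-group test | 43% | 55% | 78% | 94% |
| 1 Hz v sham, unadjusted | 62% | 74% | 90% | 98% |
| 1 Hz v sham, gate plus Holm | 36% | 49% | 75% | 94% |

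**The case against.** The case for the plan is strong on five counts.

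- **Validity.** Covariates are selected on baseline balance, not on outcomes. A reader might infer that the rule inflates false positives, but the simulated error rates show that it does not. A reader might also infer that the change-score comparison is biased. Over randomisation it is unbiased; step 4 applies only given a chance gap.
- **Scope.** A reader might infer that the primary result is affected. The primary chi-square has no covariates, so it is not. Section 4.1's wording leaves some ambiguity about SRRS change, but that is a question of endpoint definition.
- **Source of the gain.** The quoted sentence concerns descriptive parameters, whereas the gain in step 2 comes almost wholly from the outcome's baseline value. If the matching factors predict nothing, adding them slightly lowers power. Stable factors that shift both time points equally cancel in the group-by-time test.
- **Time points.** SRRS and actigraphy are also taken every five sessions (4.1, 4.3, 7.1). Step 2 assumes the two-point analysis of 6.1 and 8.5.
- **The contrast.** The hypothesis names no comparator, so 1 Hz against sham is a reading, though the natural one in a sham-controlled trial.

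All five stand as limits. None supplies the missing covariate list, imbalance criterion, contrast or multiplicity rule.

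**Conclusion.** The concern holds within these limits.

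(a) The analyses of SRRS change, actigraphy, tapping, TULIA and the symptom scales use a less precise method than the collected data allow, and their model is not fixed in advance. The harm is lost precision and an open model. The variance saving is about 35/25/15% in theory at ρ 0.3/0.5/0.7, about 31/21/10% after paying for four uninformative factors, and little or nothing at 0.9. The documents give no ρ, SD or effect size, so these are ranges under assumption.

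(b) As a secondary point, no contrast or multiplicity rule covers the inhibitory SMA hypothesis. The 17–21% and 11–13% apply only if the plural chi-square tests mean ungated pairwise tests, and only at a single final look.

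A reader might also infer that the 90% in section 8.2 holds for the four-group test and fails only for the contrast. The figures do not support that: at lower response rates neither test reaches 90%, and the unadjusted contrast has more power than the four-group test in the pattern shown.

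**What to change.** (a) In section 8.3, delete the imbalance condition. Analyse the end value of each continuous outcome by ANCOVA, always including its baseline value and the matching factors (age, gender, education, diagnosis). Omit diagnosis for the symptom scales, since each set is given to one diagnosis only. Label the ANCOVA on symptom change as exploratory, because its covariate is measured after randomisation. No new data or patients are needed. The cost is about 2–3% of variance if the matching factors predict nothing, and proportionally more in the smaller single-diagnosis analyses.

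(b) Keep the four-group chi-square as primary. Name 1 Hz SMA against sham as a prespecified contrast under a stated multiplicity rule of the sponsor's choice, for example Holm over the three active-against-sham comparisons. Make the rule consistent with the looks at 25, 50 and 75%, and say how the contrasts are handled if an arm has been stopped. Error control costs power: with 1 Hz alone working at an assumed 60 against 20%, the contrast has 75% power unadjusted and 58% with gate plus Holm.

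Section 8.2 need not change for this point. If it is revised, it should say that the 90% does not hold at lower response rates for either test.

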5.2. Inclusion criteria

Right handed patients with MDD or schizophrenia according to DSM 5, ages 18-65 years old displaying reduced motor activity screened with the Bern Psychopathology Scale (BPS) (Strik et al., 2010). BPS is a validated, quantitative and qualitative scales for the assessment of system-specific psychotic symptoms. Diagnoses will be given through application of MINI and review of complete cases records. Patients must have normal or corrected-to-normal vision and hearing.

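### Section 8.3 does not say at what covariate value time effects are tested; a covariate entered as recorded after an imbalance would put that test at covariate value zero (minor)

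*Combined protocol and SAP*

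**What the plan says.** Section 8.3 analyses changes in motor variables within and between groups by repeated-measures ANOVA: "This way, we will test for time effects and effects of stimulation protocol". The next sentence is the covariate rule: if the groups turn out to differ in descriptive parameters, "these parameters will be entered as covariates to the repeated measures ANCOVA". The diagnosis-specific symptom ratings are handled in the same way.

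Section 8.3 does not name the descriptive parameters. Section 4.3 lists what is recorded, including "Questions concerning demographic data (age, gender, education, occupational status"), together with substance use and medication. Section 4.4 states: "Groups will be matched for age, gender, education and diagnose". Section 5.2 admits patients of "ages 18-65 years old displaying reduced motor activity". Under section 6.1, "clinical ratings will be assessed twice, at baseline and after the last TMS" session.

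The protocol nowhere mentions centring, a reference value for covariates, or whether the time effect comes from the model with or without them.

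**The concern.** With two assessments, a repeated-measures ANCOVA is a linear regression of the change score on arm and covariate. The time main effect is the arm-averaged intercept, which is the expected change where the covariate equals zero. For age or years of education, zero lies outside anything the trial will observe. The test then no longer asks whether motor performance changed over the three weeks in the patients studied. It asks what a straight line predicts far below the data.

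Aim (a) in section 3.1, the effect of three weeks of daily sessions on motor performance, is read partly from this time effect. Two analysts who both follow 8.3, one centring and one not, could report opposite time effects from the same data.

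**Working it through.** **The plan's own figure.** The protocol gives a calculation only for the primary Chi² test (section 8.2). Effect size: √[(0.40 - 0.25)²/0.25 + (0.10 - 0.25)²/0.25] = √0.18 = 0.4243. With 79 patients the noncentrality is 79 × 0.18 = 14.22. With 3 df and critical value 7.815, power is 0.901. The stated 79 is reproduced, and the present point does not touch it. No figure is given for the time test.

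**Inputs from the protocol.** 80 patients, four arms of 20; two assessments; significance level 0.05 (taken as two-sided); ages 18-65.

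**Assumptions, not in the protocol.** Age mean 40, SD 12; true mean improvement 0.5 SD of the change score, improvement scored positive; correlation r between age and change.

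**Formulas.** With the change score in SD units, the slope on age is r/SD(age).
- Quantity tested with age as recorded: mean change - r × mean(age)/SD(age).
- Standard error relative to the centred model: about √[1 + (mean/SD)²].

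**Age unrelated to change (r = 0).**
- SE factor: √[1 + (40/12)²] = 3.48.
- Expected t, centred: 0.5 × √80 = 4.47, against a critical value of 1.99. Power is about 99%.
- Expected t, as recorded: 4.47/3.48 = 1.29. Power is about 23% in simulation (4 × 20 patients, 4,000 runs).

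Other assumed distributions, same true change, r = 0:

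| Covariate (mean/SD) | SE factor | Power, as recorded | Power, centred |
|---|---|---|---|
| Age 35/14 | 2.7 | 36% | about 99% |
| Age 40/12 | 3.5 | 23% | about 99% |
| Age 48/10 | 4.9 | 14% | about 99% |
| Education 13/3 years | 4.4 | 16% | about 99% |

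**Age related to change.**
- r = +0.2: 0.5 - 0.2 × 40/12 = -0.17 (simulated mean -0.16). A real improvement appears as a worsening.
- r = -0.2: 0.5 + 0.2 × 40/12 = +1.17. The improvement is more than doubled.
- The sign of the tested quantity reverses once r exceeds 0.5 × 12/40 = 0.15.

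**No true mean change.** At r = 0.2 the tested quantity is -0.2 × 40/12 = -0.67. Its SE is √(1 - 0.04) × 3.48/√80 = 0.38, so the expected t is about 1.75 in size. The simulated rejection rate is about 39%, and about 73% at r = 0.3. With centred age it is 5-6%.

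**Mode by time.** In simulation with recorded and with centred age, the F statistic for the protocol comparison was identical to rounding error (largest difference about 1e-13). Centring moves only the intercept.

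**The case against.** **The rule is conditional, and matching works against it.** A reader might infer that 8.3 always enters age and education. It names neither, and it acts only on unequal distribution. Section 4.4 matches on both, so the covariates used for the figures above are among those the plan tries to balance. This stands and lowers the chance that the problem occurs. It does not remove it, because no matching mechanism is described and arms hold only 20. Occupational status, substance use and medication are recorded but not matched. If imbalance were judged by independent 5% tests (an assumption), those three alone would give 1 - 0.95³ = 14% for at least one trigger. The size of the distortion would then depend on how that variable is coded and where its zero lies.

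**The plan is silent, not wrong.** The sentence on time effects follows the ANOVA without covariates, and the ANCOVA can be read as serving only the comparison between protocols. On that reading there is no problem. The text allows this reading but does not fix it.

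**Software.** A reader might infer that SPSS will produce the uncentred test by default. The protocol ties the package to another task: "Descriptive data analyses will be performed using Statistical Package for Social Sciences SPSS 17.0". It says nothing about how covariates are handled, and the point does not need it.

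**Categorical parameters.** Entered as between-subject factors with time averaged over their levels, they cause no such problem. Entered as numeric codes they do: with 0/1 coding the test refers to the level coded 0, and with 1/2 coding to no level at all.

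**Comparability across outcomes.** It is tempting to add that outcomes analysed with and without covariates could not be compared. Imbalance is a property of the groups, so the same covariates would normally enter every motor outcome. That extra harm is not supported, apart from diagnosis-specific subsets and missing data.

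**Conclusion.** The point holds in conditional form. If the imbalance rule is triggered, the parameter is entered as recorded, and the time effect is read from that model, the test answers a question about covariate value zero. It can then miss, reverse, inflate or invent a change. Under the assumed age distribution and a 0.5 SD change, power is about 23% instead of 99% at r = 0. The estimate is -0.16 or +1.17 SD at r = +0.2 or -0.2, and false rejection is about 39% at r = 0.2. The algebra is general; these sizes rest on assumed means, SDs and correlations.

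The consequence is minor. A reader might infer that the comparison of stimulation protocols or the trial's main result is at risk. The documents do not support that: the primary analysis is a Chi² test of response, the mode-by-time test does not change with centring, and N = 79 stands. The affected quantity is a secondary pre-post change pooled over four arms, one of them sham, and it could not be attributed to TMS even when correctly centred.

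**What to change.** Add one sentence to section 8.3:

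> Covariates entered in the repeated-measures ANCOVA because of imbalance, including indicator variables for categorical parameters, are centred at their overall sample mean, so that time effects refer to the average patient.

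Centring the indicators matters for that last phrase: effect coding with unequal level sizes would give the unweighted mean of the levels instead. Alternatively, state that time effects are taken from the model without covariates.

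Do not extend the centring to the separate ANCOVA in 8.3 that asks whether motor improvement reflects general clinical response. There the covariate is symptom change, and zero, meaning no symptom change, is the value of interest.

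The cost is one sentence. No data, patients or visits are added, and the between-protocol test is unchanged.
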